The Mobile Health platform is developed by Wellframe, a Boston, Massachusetts-based health care technology company. Wellframe aims to improve patient engagement in their health, and enable convenient, effective support by allowing for messaging between study staff and patients based on a patient's progress with their care plan. The Mobile Health platform consists of a patient held mobile app, a clinician dashboard and a suite of clinical programs with configurable rules. The patient mobile app features a personalized adaptive daily health checklist that includes reminders to patients to engage in health behaviors and a series of personalized, interactive surveys, articles, and encouragement. The app connects to the mobile device's movement sensors to facilitate a structured clinical program with physical activity monitoring. In addition, there is a patient education library with both written and video content specific to their health condition or procedure. The written patient education content is curated from evidence-based guidelines. The video content delivers standardized teaching. The App was developed using user-experience and design principles to ensure a user-friendly design for all users. The registration process is streamlined so that it only takes a few minutes to set up. In addition to requiring a password-secured account for the Mobile App, patients are encouraged through an educational article to add a passcode to their mobile device for additional security.

Wellframe Content Development

All content is derived from the government sources, or from professional society publications that have been licensed for commercial reuse or for reference and citation within documents intended for commercial use. See below for a select list of sources; all referenced sources are cited in the references section of each article that appears in the patient mobile app. Referenced sources include:

- American Heart Association
- Centers of Disease Control and Prevention

- Harvard Medical School
- MedlinePlus, U.S. National Library of Medicine
- National Institute of Diabetes and Digestive and Kidney Diseases, National Institutes of Health
- National Heart, Lung and Blood Institute, National Institutes of Health
- NIH Senior Health, National Institutes of Health

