- On the a smartphone or tablet, patients go to <http://guide.wellframe.com/> and click “Install Now” OR open the App Store (iOS) or Play Store (Android) and search for **Wellframe**.
- Install the Wellframe app on their smartphone or tablet.

STEP 2: Sign Up

- Open Wellframe and tap Create New Account.
- Type in this access code to sign up for an account: **[ACCESS CODE]**
- Patient enters demographic information (first name, last name, date of birth, gender, and telephone number), then an email and password to complete registration.
- The patients will be prompted to set up reminders for any medications they take. Enter the medication name and choose the time(s) of day they’d like to be notified to take their medications.
- They’ll be prompted to accept push notifications from Wellframe. Patients say “Yes/Accept/OK” to allow notifications for medication reminders, messages from the clinical team, and updates to instructions. These notifications will appear on the lock/home screen of the mobile device. They will never contain personal health information; they will simply prompt patients to open Wellframe for a new task, message, or instruction, e.g. “You have a task to complete (9:00 AM)” for a medication reminder.

- Lastly, when patients tap on the Physical Activity task, they'll be prompted to allow Wellframe to access motion & fitness tracking data from Apple Health Kit (iOS devices) or Google Fit (Android devices). Accepting this permission will allow Wellframe to track the patients' steps throughout the day. Wellframe cannot see patients' location; Wellframe calculates steps based on the movement of the device when the patients carry their smartphone or tablet in their hand, pocket, or bag.

Study Procedures

Study Staff and Health Advocate Role

During the study, subjects will be encouraged to complete daily tasks by the Health Advocate as described above in the Clinical Team Dashboard Purpose & Function section.

Study staff will monitor the subjects' Wellframe applications. Study staff will explain to subjects that for this study, the clinician messaging function will be used for study communications only (i.e. reminding them to enter their medications), and health advocate messaging will be for non-clinical communications about health behaviors; any clinical questions should be directed to their healthcare providers.

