Hypertension	Program on managing high blood pressure, including medications, diet, and other lifestyle factors.	
 • Pathophysiology: Causes, anatomy, complications • Symptoms: blood pressure management, cardiac precautions • Medications: Beta blockers, ACE inhibitors, diuretics, ARBs, aspirin, statins • Lifestyle: Smoking, diet, exercise, sleep, alcohol • Other: Depression, intimacy, vaccines
Diabetes	Program on managing diabetes, including monitoring, medications, and lifestyle factors.	
 • Pathophysiology: Causes, anatomy, complications • Symptoms: hypoglycemia, hyperglycemia, red flag symptoms • Medications: Oral, insulin • Lifestyle: Smoking, diet, exercise, sleep, alcohol, meal planning, calories, portion control • Other: Depression, kidney disease, foot care, eye care, oral health, falls, intimacy, vaccines
Weight Loss	Structured weight loss plan with a weekly curriculum	
 • Calories • Fiber • Portion size • Meal planning • Goal setting • Exercise • Cravings • Alcohol
Beginning Physical Activity	Structured physical activity plan with weekly goals	
 • Guidelines, safety • Making a plan • Injury prevention • Barriers

		
 • Endurance • Strength training • Balance • Flexibility
Smoking Cessation	Structured smoking cessation program	
 • Quit date • Reasons to quit • Strategies: withdrawal, cravings, meds, nicotine replacement therapy, milestones, rewards, support • Weight gain • Stress, depression
Stress	Program on recognizing and managing stress	
 • Chronic stress • Stress cycle • Triggers • Time management • Attitude, emotions • Getting help • Conflict negotiation • Anxiety, depression

To track patient reported clinical outcomes (cardiac rehabilitation and cardiology appointment attendance) through Wellframe, subjects will be asked the following questions via the survey function in Wellframe:

- At 30d: Have you attended an appointment with a cardiologist?
- At 30d: Have you scheduled an appointment for cardiac rehabilitation?
- At 60d: Have you attended an intake appointment for cardiac rehabilitation?
- At 75d: Have you attended the first exercise session for cardiac rehabilitation?

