30-day Content Completion	Percentage of content tasks (articles opened) completed within 30 days on app
90-day Content Completion	Percentage of content tasks (articles opened) completed within 90 days on app
30-day Survey Completion	Percentage of survey tasks completed within 30 days on app
90-day Survey Completion	Percentage of survey tasks completed within 90 days on app
30-day Weekly Patient Engagement	Percentage of days in which patient completed at least one task from the app checklist (survey, article, physical activity goal, encouragement) or sent a message to clinical team at least once over the previous 7 days within 30 days on app.
90-day Weekly Patient Engagement	Percentage of days in which patient completed at least one task from the app checklist (survey, article, physical activity goal, encouragement) or sent a message to clinical team at least once over the previous 7 days within 90 days on app.
30-day Daily Patient Engagement	Percentage of days in which patient completed at least one task from the app checklist (survey, article, physical activity goal, encouragement) or sent a message to clinical team within 30 days on app.

90-day Daily Patient Engagement	Percentage of days in which patient completed at least one task from the app checklist (survey, article, physical activity goal, encouragement) or sent a message to clinical team within 90 days on app.
Patient Satisfaction	Average patient response on app satisfaction via app survey function.
Patient Messages Sent	Number of total messages sent by patient within 90 days on app
Patient Messages Received	Number of total messages sent to patient within 90 days on app
Patient Messages Opened	Percentage of messages sent to patient that were opened
Patient Message Response	Percentage of messages sent to patient with at least one message response from patient
Patient Physical Activity	Percentage of days where patient met physical activity goal (default of 500 steps) within 90 days on app.
Days to First Message	Days until first message sent from care team to patient
Clinical Messages	Percentage of patients receiving at least one message from app care team within 90 days on app.

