Primary analysis will verify balance in matching (unadjusted) via Chi-squared model for binary variables and ANOVA for categorical variables

I. Engagement Analyses: Overall engagement by patients in the intervention arm with the Wellframe application will be assessed by evaluating the number of days or weeks with at least one task completed (including surveys done, content read, activity goals reached and medication reminders used) within both a 30- and 90-day period. Individual task completion rates will also be assessed and reported within 30- and 90-day periods. Use of messaging between patients and health advocates will also be assessed during a 30- and 90-day period. Changes in these metrics across 30- to 90-days will be evaluated.

J. Exploratory Analyses:

We will compare subgroups (MI/elective) using linear regression across the 30-day engagement metrics above to evaluate predictors of engagement (adjusting for both 30-day engagement as well as matching covariates such as age, sex, PCI type, state, insurance, partners PCP and site).

We will use the Cox Proportional Hazards model to assess efficacy of the intervention on lowering rate of ER visits for cardiovascular reasons, ER visits for all causes and hospitalizations for all reasons.

We will use the Cox Proportional Hazards model to assess efficacy of the intervention on reducing rates of repeat PCI, stroke, non-fatal MI, cardiovascular cause of death and all cause death within 90 days of enrollment.

We will use the Cox Proportional Hazards model to assess for improvement in percentage of patients adhering to cardiovascular follow up appointments within 30 days of discharge.

K. Type I Error Control: We will control for error by limiting our primary outcome to 90-day cardiac rehabilitation enrollment. All subsequent analysis, including secondary outcomes, will be considered exploratory.

L. References:

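### Daily and weekly engagement can be earned by meeting a sensor-counted step goal, and no engagement rate without steps is planned, so the engagement results may partly reflect walking and phone carriage

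*SAP*

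**What the plan says.** SAP D.7 defines four engagement variables: daily and weekly, each at 30 and 90 days. In all four, a qualifying day is one on which the patient "completed at least one task from the app checklist (survey, article, physical activity goal, encouragement") or messaged the clinical team. Any one of these is enough. The weekly version looks back over a rolling window; its 30-day row ends "sent a message to clinical team at least once over the previous 7 days within 30 days on app".

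The step threshold appears in a separate D.7 row, Patient Physical Activity: "Percentage of days where patient met physical activity goal (default of 500 steps) within 90 days on app". Applying the same default to the engagement rows is the natural reading, but those rows do not repeat it.

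SAP Section I describes engagement as days or weeks with at least one completed task, "including surveys done, content read, activity goals reached and medication reminders used".

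On the source of the step data, the protocol (Patient Mobile App Purpose & Function) says "The app connects to the mobile device's movement sensors to facilitate a structured clinical program with physical activity monitoring". Its onboarding text (Step 2) says "Accepting this permission will allow Wellframe to track the patients' steps throughout the day". The permission prompt appears when the patient taps the Physical Activity task in the app.

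Neither document says whether reaching the goal completes the task by itself, or whether the patient must open the app that day for the credit to register.

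**The concern.** Surveys, articles and messages need the patient to act in the app. A step goal read from a sensor may need only that the patient carries the device and walks. A measure that accepts either one mixes app use with mobility, and nothing planned separates them.

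Protocol Aim 2 names patient application engagement as a process outcome. The SAP reports it in Table 4.2 and Figure 2 and uses it in the Section J regressions, Table 4.3 and Figure 8 (predictors of engagement). Figure 7 sets daily engagement beside rehabilitation enrollment, cardiology follow-up and readmission. Age, peripheral arterial disease and MI versus elective PCI are plausibly related to walking, and walking is plausibly related to recovery. A step-credited measure could therefore show associations with these factors and outcomes that say little about use of the app.

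**Working it through.** The plan states no expected engagement rate, so there is no figure to reproduce. The question is what the definition returns if the step goal is credited automatically. All rates below are assumptions, because the documents give none.

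**Inputs**
- p: share of days on which a patient with tracking on meets the goal (assumed 20% to 90%).
- q: share of days with any active task or message (assumed 0 or 10%).
- s: share of patients who granted tracking (assumed 25% to 100%).
- Days are taken as independent, with tracking on from day 1.

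**Formulas**
- Daily engagement: a = 1 − (1 − q)(1 − p).
- Weekly engagement over T days: the mean over d = 1 to T of 1 − (1 − a)^min(d,7).
- Cohort daily engagement: s·a + (1 − s)·q.

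**No active use after set-up (q = 0), tracking on**

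| Goal-met days p | Daily | Weekly, 30 d | Weekly, 90 d | All four rates, steps excluded |
|---|---|---|---|---|
| 20% | 20% | 73% | 77% | 0% |
| 50% | 50% | 96% | 98% | 0% |
| 80% | 80% | 99% | >99% | 0% |
| 90% | 90% | >99% | >99% | 0% |

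First row, 90 days: days 1 to 6 contribute 0.200 + 0.360 + 0.488 + 0.590 + 0.672 + 0.738 = 3.049. Each of the other 84 days contributes 1 − 0.8^7 = 0.790, in total 66.384. Then (3.049 + 66.384)/90 = 0.771.

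**Effect of the window alone.** One qualifying day in every seven, the first on day 1, gives weekly engagement of 100%. Daily engagement is then 5/30 = 17% at 30 days and 13/90 = 14% at 90 days.

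**Cohort effect (q = 10%, p = 80%).** Here a = 1 − 0.9 × 0.2 = 82%. Cohort daily engagement is 28%, 46%, 64% and 82% at uptake of 25%, 50%, 75% and 100%, against 10% with steps excluded.

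**A case with little effect.** With q = 30%, p = 20% and uptake of 25%, a = 1 − 0.7 × 0.8 = 44%, and the cohort rate is 0.25 × 44% + 0.75 × 30% = 33.5%, against 30%.

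**Two related gaps in the definitions**
- Section I counts medication reminders used as a qualifying task; the D.7 engagement rows do not list them. A day on which the only activity is a medication reminder qualifies under one and not the other.
- D.7 sets medication adherence to null when no reminders were set up. Patient Physical Activity has no matching rule for patients who did not grant tracking.

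**The case against.** The strongest reply is that physical activity monitoring is part of the program, so counting its goal as engagement is an open, deliberate choice. Engagement is also a lesser endpoint: conversion rate is the protocol's primary process outcome, and SAP Section K makes everything except 90-day rehabilitation enrollment exploratory. Individual task rates are reported too. Tables 4.1 and 4.2 show content completion, survey completion, messaging and physical activity separately, so a reader could notice high engagement beside low content and survey completion.

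Much of this stands, and it is why the D.7 definition should be kept. The separate rates do not close the gap, however, because they cannot show how many days were engaged through steps alone, and the predictor analyses and Figure 7 use the combined measure.

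Four stronger readings are tempting, and the documents do not support them.
- *Patients who never open the app score as engaged.* The onboarding text requires a tap on the Physical Activity task before the tracking prompt appears. At most, the point covers patients who do not reopen the app after set-up.
- *Automatic credit is a fact.* It is an inference from all-day tracking. The vendor's software could require the app to be opened.
- *Tablet users get little credit.* The protocol says steps are calculated when a phone or a tablet is carried. Less credit for tablets is a guess about carrying habits.
- *Program 2 raises the step goal.* The Beginning Physical Activity module is described only as "Structured physical activity plan with weekly goals"; no change of step threshold is stated. Program 2 is optional and follows a first program of about 30 days, so it would not ordinarily affect the 30-day metrics.

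**Conclusion.** The point holds as a weakness of definition. A met step goal can by itself make a day engaged, the steps come from a sensor, and no step-free rate is planned. If credit is automatic, a patient with tracking on and no active use scores daily engagement equal to the share of days at goal, and 90-day weekly engagement of 77% to over 99% for shares of 20% to 90%, against 0% with steps excluded. This rests on automatic credit, independent days and assumed inputs. Positive correlation between walking and app use would narrow the gap in patients who do use the app. Across the cohort the effect scales with permission uptake and may be only a few points if uptake or walking is low.

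A reader might infer that the trial's main result is compromised. It is not: the 90-day rehabilitation comparison and its power statement do not use this variable. What is affected is the interpretation of the Aim 2 engagement rate, Section J, Table 4.3, and Figures 2, 7 and 8. The change is worth making but is not critical.

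**What to change.** 1. Keep the D.7 definition. Add daily and weekly engagement at 30 and 90 days that count only patient-initiated actions: survey, article, encouragement, message sent.
2. Use the added version in the predictor analyses (Section J, Table 4.3, Figure 8) and Figure 7, with the all-task version alongside. Adding is preferable to replacing, because the SAP is dated 12/28/19 and its own timeline ends follow-up in 09/2019; a replaced definition would be open to the charge of being post hoc.
3. State how the physical activity task is completed: automatically from the sensor, or only when the patient opens the app.
4. Reconcile D.7 with Section I on whether medication reminders count.
5. Report Patient Physical Activity among patients who granted tracking, and give that number. If individual goals were changed from the default, report it at one common step threshold.

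The cost is SAP wording and a small re-cut of vendor data. The documents do not say that day-level task data are supplied, so their availability should be confirmed first. The patient-initiated engagement rate can only be equal to or lower than the all-task rate, and the sponsor should expect that.

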A Smartphone-based Application Post-myocardial Infarction to Manage Cardiovascular Disease Risk
NCT03416920
Version Date: 12/28/19
[name], [name]
Statistical Analysis Plan

A. Background and Rationale:

The period between inpatient hospitalization for symptomatic coronary artery disease (CAD) and post-discharge office consultation remains a vulnerable interval for adverse outcomes. We sought to develop and evaluate a tool to help guide, reassure and educate patients during this susceptible time.

We aimed to recruit and onboard 150 patients who have undergone percutaneous coronary intervention (PCI) with a novel mobile health platform developed specifically for this population. The mobile application (app) includes educational about specific procedures (PCI) and diagnoses (coronary artery disease, acute myocardial infarction) as well as lifestyle education programs (hypertension, hyperlipidemia, diabetes, weight loss, smoking cessation). The app also utilizes live health care coaches to interact with participants virtually to facilitate adherence to outpatient follow up, enrollment in cardiac rehabilitation and achieve individually targeted goals.

B. Hypothesis:

Our overall hypothesis is that engagement with our smartphone application post PCI will correlate with increased rates of enrollment in cardiac rehabilitation amongst study participants as compared to historical controls.

C. Endpoints:

- C.1. Primary:** 90-day cardiac rehabilitation enrollment rates
- C.2. Secondary:** 30-day cardiac outpatient follow up attendance

D. General Study Design and Plan

- D.1. Design:** Multi-site stratified single-arm prospective study

- D.2. Type of controls:** Historical

D.2.a. Control ascertainment: Query of Research Patient Data Registry (RPDR) database (a centralized clinical data registry that gathers clinical information from various Partners hospital systems with a query tool that provides users with detailed medical record information on identified patient populations that meet user-defined characteristics and criteria such as diagnoses, procedures, medications and/or laboratory results) for subjects aged 21-85 years old who underwent percutaneous coronary intervention from 01/01/2015 through 12/31/2017.

D.2.b. Control matching: Controls matched for Age, Sex (M/F), State (MA/non-MA), PCI Type (MI/Elective), DM2 (Y/N), Partners PCP (Y/N), Insurance Type (Commercial/Medicaid/Medicare/Other), Site (MGH/BWH)

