30-day hospitalization	Admission date to a Partners hospital within 30 calendar days of incident PCI.
90-day hospitalization	Admission date to a Partners hospital within 90 calendar days of incident PCI.
Cardiac reason for hospitalization	Admission for chief complaint of cardiac etiology (ie CAD, CHF, arrhythmia), admission requiring cardiac consultation or admission to a cardiology ward unit.
30-day ER visit	Presentation to Partners ER or Urgent Care within 30 calendar days of incident PCI without subsequent hospitalization.
90-day ER visit	Presentation to Partners ER or Urgent Care within 90 calendar days of incident PCI without subsequent hospitalization.

90-day Cardiac Rehabilitation	Attendance of cardiac rehabilitation intake session at a Partners facility within 90 calendar days of incident PCI.
30-day Cardiac Follow Up	Attendance of cardiac outpatient follow up appointment at a Partners facility (with MD or NP) within 30 calendar days of incident PCI
30-day repeat PCI	Repeat percutaneous intervention on same or new coronary lesion within 30 days of incident PCI.
90-day repeat PCI	Repeat percutaneous intervention on same or new coronary lesion within 90 days of incident PCI.
90-day Stroke	Chart diagnosis of or admission for new stroke within 90 calendar days of incident PCI as noted in Partners EHR.
90-day Nonfatal MI	Chart diagnosis of or admission for myocardial infarction (without subsequent death) within 90 calendar days of incident PCI as noted in Partners EHR.
90-day CV Death	Documentation of death within 90 calendar days of incident PCI noted in Partners EHR with cause specified as secondary to CAD, CHF, Arrhythmia or other clear cardiovascular reason.
90-day All Cause Death	Documentation of death within 90 calendar days of incident PCI noted in Partners EHR.
Conversion Rate	Number of patients enrolled in Wellframe out of number of total patients eligible for study.
Days Enrolled	Number of days between patient onboarded with Wellframe app and marked done by clinical staff.
Medication Reminders	Number of medication reminders set up by patient (0 if patient has not set up any reminders).
30-day Medication Adherence	Percentage of medication reminder tasks completed within 30 days on app. (Null if no patient reminders set up)
90-day Medication Adherence	Percentage of medication reminder tasks completed within 90 days on app. (Null if no patient reminders set up)

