D.8. Sample size and power: We have at least 95 percent power with 150 enrolled participants, 450 matched historical controls, with alpha equal to 0.05, to detect an effect of at least 2-fold increase in the primary clinical outcome, likelihood of enrollment in cardiac rehabilitation within the 90 day study period with baseline 25% enrollment rates⁶.

E. General Considerations:

E.1. Analysis populations:

E.1.a.: Full analysis population: All intervention subjects who downloaded the study application and 3:1 matched historical controls.

E.1.b.: Engagement population: All intervention subjects who downloaded the study application.

E.2. Covariates and subgroups: Sex (M/F), State (MA/non-MA), PCI Type (MI/Elective), DM2 (Y/N), Partners PCP (Y/N), Insurance Type (Commercial/Medicaid/Medicare/Other)

E.3. Missing data: Missing data values for participants who fit inclusion criteria will default to zero or “no” for dichotomous variables. Missing data values for participants will default to “unknown” or “other” for continuous or categorical variables.

F. Summary of study data: All continuous variables will be summarized using the following descriptive statistics: n (non-missing sample size), mean, standard deviation, median, maximum and minimum. The frequency and percentages (based on the non-missing sample size) of observed levels will be reported for all categorical measures. In general, all data will be listed, sorted by site, treatment and subject, and when appropriate by visit number within subject. All summary tables will be structured with a column for each treatment in the order (Control, Experimental) and will be annotated with the total population size relevant to that table/treatment, including any missing observations.

G. Protocol deviations: Subjects who do not fit inclusion criteria will be removed from the data set prior to analysis. Subjects with missing data will be treated as discussed above (Section E.3.)

H. Efficacy Analyses: The Cox Proportional Hazards model will be used to assess efficacy of the intervention (use of the application) on the primary outcome. The percentage of subjects attending cardiac rehabilitation enrollment within 90 days of discharge from incident PCI hospitalization will be compared across groups. A secondary analysis between the two groups will be conducted adjusting for covariates such as age, sex, insurance type, state, diabetes, and partners PCP).

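### The primary endpoint is a 90-day enrolment proportion, but the only efficacy model specified is Cox, and no effect measure, interval, test or adjusted estimate is given on the proportion scale

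*SAP*

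**What the plan says.** SAP C.1 names the primary endpoint as "90-day cardiac rehabilitation enrollment rates". D.7 makes it a yes/no variable: "Attendance of cardiac rehabilitation intake session at a Partners facility within 90 calendar days of incident PCI". D.8 sizes the study on the same scale: "to detect an effect of at least 2-fold increase in the primary clinical outcome, likelihood of enrollment in cardiac rehabilitation". It assumes 25% in the control group and claims power of 95% or more from 150 app patients and 450 controls at a 0.05 level. Sidedness is not stated.

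Section H then says: "The Cox Proportional Hazards model will be used to assess efficacy of the intervention (use of the application) on the primary outcome". Its next sentence commits to comparing the 90-day percentages between groups, but names no test, effect measure or interval. The adjusted analysis in H lists covariates without changing the model. In the table shells, item 2 lists three models for the primary outcome, one univariate and two multivariate, and all are Cox. Shell 2.A carries a Cox label over a caption that describes a percentage of patients.

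Two other outputs show the proportion. F promises frequencies and percentages for categorical measures, by group, and the figure list includes a bar plot of enrolment. D.7 defines no time-to-intake variable and no censoring rule. It counts the 90 days from PCI, whereas H counts them from discharge. E.3 sets a missing yes/no value to no, so every patient has an analysable day-90 status.

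**The concern.** The question asked is how many more patients are enrolled by day 90. The one specified model answers a different question: how the rate of intake compares at each moment among patients not yet enrolled. The two answers part company in two ways.

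First, the outcome is common (25% expected, 50% under the target), so a hazard ratio above 1 is larger than the corresponding ratio of proportions. Second, a hazard ratio responds to when intake happens as well as to whether it happens by day 90. If coaching brings intake forward without adding a single enrolled patient, the Cox model moves towards benefit although the stated endpoint has not changed. K rests all type I error control on this one outcome, so H should be clear about which quantity is tested and reported.

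**Working it through.** **Inputs from the SAP.** 150 app patients and 450 controls (D.8; "3:1 matched historical controls" in E.1.a), alpha 0.05 (taken as two-sided), control proportion 0.25, and target proportion 0.50, reading D.8 as a risk ratio of 2.

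**1. The plan's own power figure.** Pooled proportion = (112.5 + 75)/600 = 0.3125.
- Null SE = √[0.3125 × 0.6875 × (1/150 + 1/450)] = 0.0437.
- Alternative SE = √[0.50 × 0.50/150 + 0.25 × 0.75/450] = 0.0456.
- z = (0.25 − 1.96 × 0.0437)/0.0456 = 3.60, so power is 99.98%.

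If two-fold meant HR 2, expected events are 450 × 0.25 + 150 × 0.4375 = 178.1. Schoenfeld's formula gives z = ln 2 × √(178.1 × 0.25 × 0.75) − 1.96 = 2.05, so power is 98.0%. The claim of at least 95% holds on both readings. An odds ratio of 2 (25% to 40%) would give 93.0%, but D.8 does not speak of odds.

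**2. Hazard ratio against fold-increase.** Under proportional hazards p₁ = 1 − (1 − p₀)^HR.
- HR 2.0 from 25%: 1 − 0.75² = 0.4375, and 0.4375/0.25 = 1.75.
- A doubling to 50%: HR = ln 0.50/ln 0.75 = 2.41.
- For HR 2 the fold-increase is 2 − p₀: 1.85 at a control proportion of 15%, 1.80 at 20%, 1.70 at 30%, 1.60 at 40%.

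**3. Earlier intake only.** Set 25% enrolled by day 90 in both groups and censor the rest at day 90. The documents give no intake times, so the uniform ranges below are assumptions. The HR is from a large-sample fit. Rejection rates are from 10,000 simulated trials of 150 against 450, with an unadjusted Cox fit and a pooled two-proportion test.

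| Intake days, app vs control | HR | Cox, two-sided rejection | Cox, in favour of app | Proportions, two-sided rejection |
|---|---|---|---|---|
| 0–90 vs 0–90 | 1.00 | 4.3% | 2.4% | 4.6% |
| 0–60 vs 0–90 | 1.05 | 6.7% | 5.4% | 5.0% |
| 0–45 vs 0–90 | 1.08 | 8.7% | 7.6% | 5.2% |
| 10–60 vs 30–90 | 1.11 | 9.7% | 9.0% | 4.6% |
| 14–45 vs 45–90 (no overlap) | 1.16 | 14.3% | 13.8% | 4.8% |

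A separate run of 4,000 trials with complete separation gave 15.2%, which sets the top of the quoted range.

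The last row is the ceiling, and can be checked by hand. If every app intake precedes every control intake, the large-sample Cox equation for θ = HR is (0.75/θ) ln[(0.25θ + 0.75)/(0.1875θ + 0.75)] = 0.1875θ ln[(0.1875θ + 0.75)/(0.1875θ + 0.5625)]. At θ = 1.157 both sides equal 0.0468.

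The effect grows with enrolment. At 50% in both groups, days 0–45 vs 0–90 give an HR of about 1.20 with 31% rejection, and no overlap gives about 1.43 with 70–72%.

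**The case against.** The SAP does not ignore the proportion. H commits to comparing percentages, F tabulates them by group, and a reader could form a crude risk ratio from the table. That stands, and it narrows the gap to what is absent: a named effect measure, interval, test and adjusted estimate.

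The Cox model is also not without merit. It uses intake timing, it can censor at death, and it is a valid test when the app changes neither timing nor enrolment. The E.3 default makes day-90 status complete by imputation, which does not show that follow-up was complete. Earlier intake may itself matter, given the rationale in section A about the vulnerable interval after discharge. All of this is fair, but it argues for Cox as a supportive analysis, because earlier intake is not the endpoint in C.1.

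The timing effect is modest at the planned enrolment. The standard error of the log HR is about 0.19, so even the ceiling of 1.16 is a shift of ln 1.157/0.19 ≈ 0.8 standard errors. That also stands. If intake were later in the app group, the shift would go the other way.

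Finally, a reader might infer that the SAP plans to present an HR of 2 as a doubling of enrolment. It does not say so: D.8 attaches the two-fold figure to the likelihood of enrolment. The 1.75 matters only if someone reads an HR that way. The risk is not fanciful, since shell 2.A puts a percentage caption under a Cox label and J uses Cox to assess an improvement in a percentage.

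**Conclusion.** The point holds as a mismatch of scale with an unspecified comparison on the scale that matters. The endpoint and power are proportions, the only specified efficacy model is Cox, and nothing inferential is defined for the proportion.

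An HR of 2.0 would correspond to a 1.75-fold rise, given proportional hazards and 25% control enrolment. Earlier intake alone, at 25% enrolment in both groups, would give an HR of about 1.05 to 1.16 and two-sided rejection of about 7 to 15%, against about 5% for a test of proportions. These figures rest on assumed intake times, and 1.16 is the limiting case rather than a typical one.

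Two stronger readings are not supported. The sample size is not undermined: power is at least 95% whether two-fold is a risk ratio or a hazard ratio. Nor could timing alone produce anything near an HR of 2 at the planned enrolment. This is a change that should be made, not a flaw that invalidates the design.

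**What to change.** In SAP H, make the primary estimate the 90-day risk difference and risk ratio, each with a 95% CI and with standard errors that respect the matched sets (for the ratio, for example, modified Poisson regression with robust errors by matched set). State the test and its sidedness. Give an adjusted version with the covariates already listed, and add these estimates to shell 2.A.

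Keep the Cox model as supportive, with time origin and censoring defined, and do not describe a hazard ratio as a fold-increase in enrolment. Reconcile the 90-day clock, which runs from PCI in D.7 and from discharge in H.

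The cost is SAP wording and one extra model per table, with no new data. If the app works, the reported ratio will be somewhat smaller than the hazard ratio. D.5.a ends follow-up in 09/2019 and the SAP is dated 12/28/19, so the change should be dated and should state whether outcome data had been seen.
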